## 3. Study Procedures

### a. Study design, including the sequence and timing of study procedures

This is a prospective, randomized, unblinded, controlled study in the Harriet Lane Clinic (HLC), the Johns Hopkins Children's Center pediatric primary care resident teaching practice and the Johns Hopkins Children's Center Pediatric Emergency Department (Peds ED). The HLC has clinics for acute care (e.g., sick visits) and continuity (e.g., well child and follow-up visits). We will purchase Cellsopes, iPhones, phone cases, and locking storage systems for each setting. There will be no direct collaboration between the study investigators and Cellscope related to this study. We will evaluate the above aims by block-randomizing in 2-week blocks: 1 week where the Cellscope will be available and 1 week where only traditional otoscopy will be available. Because residents rotate through the HLC and Peds ED in 2 and 4-week rotations, this will allow for the inclusion of the same trainees in each arm to act as their own control and ensure there is no use of the Cellscope during the traditional-only weeks. During Cellscope weeks, the traditional direct otoscopes will be available based on trainee/supervisor preference. During the traditional weeks, the Cellscope will not be available, thus the standard of care will not be changed during our study. iPhones will be secured with 6-digit numeric passcodes, in compliance with JHMI security standards. Recordings/images of external and middle ear structures will be obtained in a HIPAA compliant manner without collecting any PHI.

During Cellscope weeks, trainees and supervisors will be given access to the Cellscope and asked to use this tool for their otoscopic exams (research procedure). They will have full discretion of when an otoscopic examination is indicated, based on their existing practice and standard of care. We will then ask that the

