If patients are interested in participating the trainees or supervisors will obtain informed verbal consent from the parent or legal guardian of the patient prior to examining the child. Explaining the study, obtaining consent, answering questions, and assessing parent and patient understanding is expected to take under 5 minutes, which is typical for a similar conversation clinical setting. A copy of the IRB protocol will be provided upon request. A waiver of written consent is requested because the consent document is the only record linking the subject and the research. The research presents no more than minimal risk of harm to subjects and involves no procedures for which written consent is normally required outside of the research context.

i. Provider Training

Providers will be trained on setting up the Cellscope: attaching the case to the iPhone, attaching the Cellscope to the case, turning on the iPhone and unlocking it. They will also be trained on how to use the Cellscope application to record non-PHI containing images/videos. This training will be done by members of the study team who are proficient in using the device and app. This will occur in whatever clinical setting, in which they are assigned (Pediatric Emergency Room, Harriet Lane Acute Clinic, Harriet Lane Continuity Clinic). This will take place prior to them using the device on any patients for the purposes of this study or any other indication.

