**5. Study Statistics**

a. Primary outcome variable.

Aim 1:

- A. Inter-rater reliability between trainee and supervisor utilizing the OMgrade scale

Aim 2:

- A. Rates of patients who receive antibiotics

- B. Levels of provider confidence in exam based on a standardized confidence measure

Aim 3: Rate of repeat exams by supervisors with and without Cellscope

b. Secondary outcome variables.

Aim 4: Rate of provider decided use of traditional otoscopy during Cellscope weeks

c. Statistical plan including sample size justification and interim data analysis.

Descriptive statistics will be performed to analyze our outcome measures in conjunction with Johns Hopkins BEAD Core statisticians.

1. Calculation of descriptive statistics such as mean, median, SD, range will be employed.
2. Examination of graphs such as outcome vs. time, scatterplots of two variables, Kaplan-Meier curves.
3. Estimation of differences between two groups with comparison by t-test or Mann-Whitney test.
4. Estimation and testing of within-person changes by matched t-test or Wilcoxon signed-rank test.
5. Multiple linear regression, logistic regression, or Cox proportional hazards regression.
6. Repeated measures models (usually requires the help of a statistician).
7. Comparison of proportions by the determination of kappa values will be employed.
8. Sample size will be calculated with an alpha of 0.05 and power of 80% to detect a change of 10%.  
We will have a minimum sample size of 392 subjects based on this calculation.

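### Three clinical settings are combined, but the analysis plan gives setting no role and the listed card items do not include it; the likely cost is modest lost precision and exposure to uneven enrolment

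*Combined protocol and SAP*

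**What the plan says.** Section 3a places the study in the Pediatric ED and the Harriet Lane Clinic and separates two kinds of visit within the latter: "The HLC has clinics for acute care (e.g., sick visits) and continuity (e.g., well child and follow-up visits". Section 3i (Provider Training) lists the three settings by name: "Pediatric Emergency Room, Harriet Lane Acute Clinic, Harriet Lane Continuity Clinic". Section 4 admits all ages, has no exclusions, and takes any patient whom the clinical team judges to need otoscopy.

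Allocation in section 3a is by "block-randomizing in 2-week blocks: 1 week where the Cellscope will be available and 1 week where only traditional otoscopy will be available". The text does not say whether the three settings share one schedule or are randomized separately.

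The card items listed in section 3a are OMgrade agreement, trainee confidence, antibiotic prescription, conversion to the traditional otoscope and repeat exam. Setting is not in that list.

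Section 5c is a list of methods with none assigned to an aim. Item 3 is "Estimation of differences between two groups with comparison by t-test or Mann-Whitney test". Items 4 to 6 add matched within-person tests, linear, logistic or Cox regression, and repeated-measures models, with no covariates named. Item 7 is "Comparison of proportions by the determination of kappa values will be employed". Setting does not appear as a stratum, covariate or subgroup.

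**The concern.** Antibiotic prescribing, and probably repeat exams and confidence, can be expected to differ between sick visits and well-child visits. An unadjusted two-group test then has two weaknesses. First, differences between settings stay in the error term and widen the interval for the device effect even when the arms have the same mix. Secondly, if the arms return different proportions of cards from each setting, the crude difference absorbs part of the difference between settings.

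The second route is open because the study is unblinded (section 3c), clinicians decide when otoscopy is indicated (section 3a), and the same clinicians obtain consent (section 3h). Alternating weeks balance calendar time; they do not control how many cards each setting returns in each arm.

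Kappa has a related difficulty. It depends on how common disease is, so the same rater performance gives different values in a sick-visit clinic and a well-child clinic.

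If setting is not recorded on the card, it may not be recoverable afterwards, because the data are collected with few identifiers.

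**Working it through.** **The plan's own figure.** Section 5c states: "Sample size will be calculated with an alpha of 0.05 and power of 80% to detect a change of 10" per cent, and then "We will have a minimum sample size of 392 subjects based on this calculation". No baseline rate is given, nor whether 392 is a total or a number per arm, so the inputs do not fix it. With z-values summing to 2.8, it matches two readings:

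- per arm at maximum variance: 2 × 2.8² × 0.25 / 0.10² = 392;
- total at 10% against 20%: (0.09 + 0.16) × 2.8² / 0.10² = 196 per arm, 392 in all.

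I take 392 as a total, 196 per arm. The variance shares below do not depend on this choice.

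**Assumptions (none is in the documents).** Equal shares of visits from the three settings. Antibiotic rates for ED / acute / continuity of 25/30/5% (base), 20/25/15% (low contrast) and 30/40/5% (high contrast).

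**Step 1: precision.** Share of variance due to setting = Σw(p − p̄)² / [p̄(1 − p̄)]. Equivalent extra visits = 392 × [1/(1 − share) − 1].

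| Rates | p̄ | Between-setting variance | Total variance | Share | Extra visits |
|---|---|---|---|---|---|
| 20/25/15% | 0.20 | 0.0017 | 0.16 | 1.0% | 4 |
| 25/30/5% | 0.20 | 0.0117 | 0.16 | 7.3% | 31 |
| 30/40/5% | 0.25 | 0.0217 | 0.1875 | 11.6% | 51 |

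In the base case the standard error of the arm difference is √(2 × 0.16/196) = 4.04 points without setting and √(2 × 0.1483/196) = 3.89 points with it. A second set of assumed rates (20/15/10%, 30/25/10% and 40/30/5%) gives shares of 1.3%, 4.3% and 11.6%, which is the same range.

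**Step 2: shift from an uneven mix.** Suppose one arm has a continuity share 10 points higher, taken equally from the other two settings. Shift = 0.10 × [(ED + acute)/2 − continuity].

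- Base: 0.10 × (27.5 − 5) = 2.25 points.
- Low: 0.10 × (22.5 − 15) = 0.75 points.
- High: 0.10 × (35 − 5) = 3.0 points.

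If the whole 10 points move between continuity and ED, the second set of rates gives 1.0, 2.0 and 3.5 points. All of these compare with a target change of 10 points. With equal mix the shift is zero.

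**Step 3: does chance imbalance invalidate the crude test?** With independent visits, the SD of the arm difference in a one-third share is √(2 × (1/3)(2/3)/196) = 4.8 points. A difference beyond 10 points then has probability about 4% (about 14% with an assumed design effect of 2 for week). The crude standard error already contains this variation. Simulating the base case with random mix, independent visits and no device effect, the crude two-proportion test rejects in about 5% of trials, as it should.

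**Step 4: kappa.** Assume a binary AOM call, both raters with 80% sensitivity and 90% specificity, and prevalence 30/30/5%. The kappas by setting are 0.48, 0.48 and 0.20. A kappa computed across settings is 0.450 with a 28% continuity share and 0.434 with 38%, a shift of 0.016. The simulated SD of the arm difference in that kappa is about 0.104, so the shift is about 15% of one SD. Combining setting-specific kappas gives an SD of 0.109 with equal weights and 0.105 with inverse-variance weights, so stratifying brings no gain in precision.

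**The case against.** The strongest reply is that section 5c does not commit to an unadjusted analysis. Items 4 to 6 list matched tests, regression and repeated-measures models, and the last two could carry a setting term. That is correct: the gap is an unspecified covariate, and part of a wider one, since no method is tied to any aim. It does not close the point. A list without covariates permits a crude test, or an adjustment chosen after the data are seen. Nor does matching on trainee settle it, because section 1 lets one trainee work in both Harriet Lane clinics.

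A second reply is that the design tends to balance the mix: each 2-week block contains one week of each kind, and the same trainees appear in both arms. This stands if every setting has both weeks, and the documents show no imbalance.

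Three stronger readings are tempting and not supported:

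- A reader might infer that the results will be biased by setting. The documents show no uneven mix, and step 3 shows that chance imbalance leaves the crude test valid when visits are independent.
- A reader might infer that Aim 1 rests on a single kappa pooled over settings. Item 7 speaks of kappa values and does not say whether they are pooled.
- A reader might infer that setting is already known for every card, because devices and training are organised by setting. The listed card items do not include it.

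The kappa figures also use a binary call, whereas Aim 1 uses the OMgrade scale, so they illustrate the dependence on prevalence and do not measure it for the planned outcome.

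**Conclusion.** The point holds as a specific, inexpensive improvement. The plan combines three settings with different visit types and does not say how setting enters the analysis. The likely harm is modest lost precision, about 1% to 12% of the variance of the antibiotic outcome, plus a vulnerability: 1 to 3 points on the crude antibiotic difference for each 10-point difference in continuity share, should uneven unblinded enrolment produce one.

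These sizes rest wholly on assumed rates and equal setting shares. No figure can be given for confidence or repeat exams without further assumptions, though the reasoning is the same. For kappa the effect on the between-arm comparison is small; the reason to look by setting is interpretation.

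**What to change.** - **Card:** add a tick-box or pre-printed field for Pediatric ED, Harriet Lane acute or Harriet Lane continuity.
- **Section 5c:** state that the between-arm comparisons for outcomes 2A (antibiotics), 2B (confidence) and Aim 3 (repeat exams) include setting as a stratum or fixed effect. Report antibiotics and repeat exams as setting-adjusted risk differences. The variance reduction above applies on that scale; a logistic coefficient would be a conditional odds ratio, which is a different estimand.
- **Aim 1:** report kappa by setting and arm as a descriptive supplement.
- **Section 3a:** say whether the settings share one schedule or are randomized separately.

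The cost is two degrees of freedom, one extra card field and some wording. Setting-level kappas will be imprecise in the smallest setting. No additional patients are needed.

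### Item 7 assigns kappa to the comparison of proportions, and no outcome has a stated between-arm analysis, including the change in agreement that Aim 1 is about

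*Combined protocol and SAP*

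**What the plan says.** Section 5a names four primary outcomes:

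- Aim 1: "Inter-rater reliability between trainee and supervisor utilizing the OMgrade scale"
- Aim 2A: "Rates of patients who receive antibiotics"
- Aim 2B: "Levels of provider confidence in exam based on a standardized confidence measure"
- Aim 3: "Rate of repeat exams by supervisors with and without Cellscope"

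Section 2 frames Aim 1 as a question of improvement: does the device make trainees more accurate, with the supervisor as reference? Section 3a randomises the order of one Cellscope week and one traditional week within each 2-week block. Every primary outcome is therefore a contrast between two kinds of week.

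Section 5c lists the methods. Item 3 is "Estimation of differences between two groups with comparison by t-test or Mann-Whitney test" and item 4 is "Estimation and testing of within-person changes by matched t-test or Wilcoxon signed-rank test". Item 5 offers linear, logistic or Cox regression, item 6 offers repeated measures models, and item 7 is "Comparison of proportions by the determination of kappa values will be employed". No item is linked to an aim.

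**The concern.** Kappa needs two ratings of the same exam. Antibiotic and repeat-exam rates in Cellscope and traditional weeks come from different visits, so there is no pair to agree or disagree. Read literally, item 7 gives two primary outcomes a statistic that cannot answer them.

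For Aim 1 kappa is a natural within-arm summary, but the aim needs a contrast. Two kappas printed side by side, without an interval for their difference, do not show whether agreement changed or whether the gap is chance.

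Read as a menu, the list leaves the method for each primary outcome open until the data are in. It also does not say that the unit of randomisation, the week within a 2-week block, will enter the analysis.

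**Working it through.** **1. The plan's own figure.** Section 5c item 8 gives alpha 0.05, power 80%, a change of 10% and a minimum of 392 subjects. No base rate is stated. With proportions near 50%, 2 × 0.25 × (1.96 + 0.84)² / 0.10² = 392 *per arm*. As a *total*, the nearest match is 10% against 20% (199 per arm, 398 in all). The wording reads as a total but the arithmetic fits per arm better, so both 196 and 392 per arm are carried below.

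**2. Kappa does not measure a difference in rates.** Take two binary tables in which both raters have the same event rate:

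| Event rate | Both yes | Each discordant cell | Both no | Observed agreement | Chance agreement | Kappa |
|---|---|---|---|---|---|---|
| 20% | 0.136 | 0.064 | 0.736 | 0.872 | 0.680 | 0.192/0.320 = 0.60 |
| 40% | 0.304 | 0.096 | 0.504 | 0.808 | 0.520 | 0.288/0.480 = 0.60 |

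The rate doubles and kappa does not move. Raw agreement does differ, which is why it should be reported beside kappa for Aim 1.

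**3. Two kappas without an interval (illustration).** The assumptions are a binary rating, equal rater marginals, independent pairs, kappa k of 0.4-0.8 and prevalence p of 10-50%. None of these values is in the documents. The large-sample variance of kappa is f/n, with

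f = (1−k) × [(1−k)(1−2k) + k(2−k)/(2p(1−p))].

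- k = 0.4, p = 0.1: f = 0.6 × (0.12 + 3.556) = 2.205
- k = 0.8, p = 0.5: f = 0.2 × (−0.12 + 1.92) = 0.360

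With equal true kappas, the chance of an observed gap of 0.10 or more is 2[1 − Φ(0.10/√(2f/n))]:

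| n per arm | k = 0.4, p = 0.1 | k = 0.8, p = 0.5 |
|---|---|---|
| 196 | z = 0.667, 51% | z = 1.650, 10% |
| 392 | z = 0.943, 35% | z = 2.333, 2% |

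For true kappas 0.1 apart, the 95% half-width of the difference is 1.96 × √((f₁+f₂)/n). At 196 per arm it runs from 0.131 (0.7 against 0.8, p = 0.5) to 0.290 (0.4 against 0.5, p = 0.1). At 392 per arm it runs from 0.092 to 0.205. For an assumed ordered scale of 3-6 grades, unweighted or weighted, it is 0.07-0.33 and 0.05-0.24.

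**4. The two rates.** With independent visits the half-width of a risk difference is 1.96 × √(2p(1−p)/n). For rates of 10-50% this is 0.059-0.099 at 196 per arm and 0.042-0.070 at 392 per arm.

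**5. Sensitivity to week effects (illustration only).** Nine to twelve months (Section 3b) is 19.6 to 26.1 two-week blocks, if all sites switch together. With an assumed week ICC of 0.01-0.05, simulation put the type I error of an unclustered t-test at about 6-11% (196 per arm) and 7-17% (392 per arm). A block-clustered standard error with a t critical value stayed near 5%. As a rough check, at 196 per arm, 19 blocks and ICC 0.05 there are 10.3 visits per week, the design effect is 1 + 9.3 × 0.05 = 1.47, and 2[1 − Φ(1.96/√1.47)] is about 11%. Neither the ICC nor a common switch is in the documents.

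**The case against.** The strongest reply is that item 7 is loosely worded rather than mistaken. Aim 1 is the only primary outcome defined as inter-rater reliability, and nothing connects item 7 to antibiotics or repeat exams. This stands. A reader might infer that the investigators intend to compare antibiotic rates by kappa, but the documents do not show that.

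A second reply is that usable methods are on the list. Logistic regression or a repeated measures model can contrast the rates. Section 3a lists agreement among the recorded outcomes, so if it is scored exam by exam, items 3, 5 or 6 could test it by type of week. This also stands: it would be too strong to say that Aim 1 or the rates have no available test. What remains is that no method is assigned, no comparison of kappas is specified, and no analysis is tied to the blocks.

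A third reply is that statisticians will be involved. Section 5c mentions them for descriptive statistics, which does not fix a between-arm comparison in advance.

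A reader might also infer that the trial is underpowered for Aim 1 or that its error rate is inflated. The documents support neither. They give no kappa, prevalence, number of grades or week-to-week variation, and they do not say that an unclustered test will be the analysis.

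**Conclusion.** The point holds in a limited form. Item 7 as worded is wrong for Aims 2A and 3 and sound only as a within-arm summary for Aim 1. The plan specifies no between-arm comparison of kappas, although Aim 1 is a question about improvement. Suitable methods for the rates and for per-exam agreement are listed but not assigned to outcomes or tied to the randomised blocks.

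The textual conclusion needs no assumption. Its size does: the 10-51% and 2-35% chances of a spurious 0.10 gap rest on the assumed binary rating, independent pairs, kappas and prevalences, and on whether 392 is the total or per arm. The week-ICC figures are a sensitivity illustration and add no weight to the conclusion. This should be corrected before analysis; it is not a flaw in the design.

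**What to change.** Restrict item 7 to Aim 1 and state one analysis per primary outcome.

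- **Aim 1.** Report kappa on OMgrade in each arm, with weights fixed in advance if the scale is ordered, and the Cellscope-minus-traditional difference with a 95% interval that respects the 2-week blocks. One workable choice is a block bootstrap standard error with a t critical value on blocks minus 1 degrees of freedom. In simulation (72 scenarios of 1,000 trials) its coverage was 92.3-96.1%, so slightly low in some settings; the percentile interval did worse, at 89.3-95.0%. The script must handle resamples in which kappa is undefined. Report the between-arm difference in raw agreement beside it.
- **Aims 2A and 3.** Report a risk difference or odds ratio with a 95% interval from the listed logistic or repeated measures model, clustered on 2-week block with a small-sample correction.
- **Aim 2B.** Report the between-arm difference in confidence with a 95% interval from the linear or repeated measures model, clustered the same way.
- **Limits to state.** Patients, trainees and supervisors who recur across blocks are not modelled unless codes are recorded. Item 4's within-person tests likewise need a trainee code. Section 3a lists the card's outcomes, not necessarily every field, so codes may already exist. A patient code would have to be checked against Section 3h, where the request to waive written consent relies on there being no other link between subject and study.

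**Cost.** SAP wording, a short script and the study week on each card; no extra patients are needed to report these intervals. Intervals widen. The t value alone adds 5-7% (2.06/1.96 at 26 blocks, 2.10/1.96 at 19). In the simulations the Aim 1 interval was 2-26% wider than the independent-pairs interval at 196 per arm and 2-43% wider at 392 per arm. The intervals for the two rates were about 3-30% wider and up to about 50% wider respectively, for an assumed week ICC of 0-0.05. The block counts assume that all sites switch together, which the plan should state.

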trainees and supervisors each fill out an index card survey to record the following outcomes: agreement between trainee and supervisor using the OMgrade scale (validated otitis media diagnostic tool), trainee confidence in exam, antibiotic prescription, need for conversion to traditional otoscopy, and whether a repeat exam was obtained. During the traditional weeks, the Cellsopes will be unavailable, locked in an enclosure, and traditional otoscopy (routine care) will be the only method available. The same index card survey will be completed by the trainees and supervisors. There will be no change to patient restraint, as described above.

b. Study duration and number of study visits required of research participants.

The study will last for between 9-12 months depending on the number of patients enrolled. Only one study visit is required per research participant. The same patient will be able to be included in the study multiple times if they present to the HLC or Peds ED on multiple occasions.

c. Blinding, including justification for blinding or not blinding the trial, if applicable.

This study will be unblinded. It is not possible to perform this study in a blinded manner given the obvious difference in the handheld hardware.

d. Justification of why participants will not receive routine care or will have current therapy stopped.

Standard of care is traditional direct otoscopy, as described above. We are using an equivalent method of otoscopy that allows the identical visualization of the external and middle ear structures. It will also be explicitly stated to providers that they can revert to traditional otoscopy if they feel that the Cellscope is not able to identify the needed structures.

e. Justification for inclusion of a placebo or non-treatment group.

N/A

f. Definition of treatment failure or participant removal criteria.

If any provider feels that the Cellscope is not able to appropriately identify the needed ear structures, that will be considered a failure of the Cellscope, and that provider will be able to immediately revert to a traditional otoscope. Furthermore, patients and guardians may opt for providers to use the traditional otoscope at any time. This will be tracked.

g. Description of what happens to participants receiving therapy when study ends or if a participant's participation in the study ends prematurely.

Resumption of traditional care, without any harm to the patient.

h. Informed Consent

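### Does the unexplained minimum of 392 subjects have to be recalculated or changed?

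*Combined protocol and SAP*

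**What the plan says.** The whole sample size justification is item 8 of section 5c: "Sample size will be calculated with an alpha of 0.05 and power of 80% to detect a change of 10" percent, followed by "We will have a minimum sample size of 392 subjects based on this calculation". Section 5a lists four primary variables. For Aim 1 it is "Inter-rater reliability between trainee and supervisor utilizing the OMgrade scale"; for Aim 2, the antibiotic rate and provider confidence; for Aim 3, how often supervisors re-examine. Item 7 of section 5c adds: "Comparison of proportions by the determination of kappa values will be employed".

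Three other places bear on the number. Section 3b says "The study will last for between 9-12 months depending on the number of patients enrolled" and also "The same patient will be able to be included in the study multiple times". Section 3h asks to waive written consent on the ground that "the consent document is the only record linking the subject and the research". Section 3a lists what the survey cards capture, starting with "agreement between trainee and supervisor using the OMgrade scale"; no patient identifier is on that list.

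**The concern.** A sample size is normally checked by putting its inputs back into a formula. Here alpha, power and a 10% change are given, and everything else is missing. Different completions lead to different enrolment targets: 392 examinations if the number is a total, 784 if it is per condition. Because study length depends on enrolment, a team could in principle stop at half of what was intended. With four primary variables and no outcome named, a reader also cannot tell which of them the 80% power belongs to. For Aim 1 a further ambiguity arises, because ten points of raw agreement and 0.10 of kappa are not the same change.

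The unit adds to this. Item 8 counts subjects, section 4 lists providers as well as patients under inclusion, and the same child can be entered more than once. With written consent waived and no study code described, it is unclear how distinct patients would be counted.

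**Working it through.** **Inputs.** From item 8: alpha 0.05, power 80%, change 10%. From section 3a: alternating weeks, so 1:1 allocation is assumed. Base rates, sidedness and independence of examinations are assumptions, because the documents state none of them. For a two-sided test, (1.960 + 0.842)² = 7.849.

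**Reproducing 392.**

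- *As a total, 10 vs 20% (or 80 vs 90%), unpooled variance.* n per condition = (p₁q₁ + p₂q₂) × 7.849 / d² = (0.09 + 0.16) × 7.849 / 0.01 = 196.2, so 392.4 in total. With pooled null variance it is 199 per condition, 398 in total.
- *Per condition, 45 vs 55%, pooled variance.* n = (1.960√0.50 + 0.842√0.495)² / 0.01 = 391.3, so 392 per condition and 784 in total. The maximum-variance shortcut, 2 × 0.25 × 7.849 / 0.01, gives 392.4 per condition.
- *As a total, one-sided, 15 vs 25%.* Unpooled, 389.5 in total; pooled, 394.
- *Paired (McNemar) with 50% discordance.* (1.960√0.50 + 0.842√0.49)² / 0.01 = 390 pairs.

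So 392 is an ordinary result under several standard readings, and the given inputs do not choose among them. A relative 10% decrease reaches 80% power with these numbers only from base rates of about 93% (392 in total) or 83% (392 per condition). There the drop is 9.3 or 8.3 points, close to an absolute 10-point change. At lower base rates the relative reading needs far more: 3,130 in total at 50% and 12,078 at 20%. An absolute change is thus the more sensible way to read item 8.

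**What 392 buys under each label.** Power = Φ{(d√n − 1.960√(2p̄q̄)) / √(p₁q₁ + p₂q₂)}, two-sided, absolute 10 points:

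| Rates | 392 in total (196 per condition) | 392 per condition |
|---|---|---|
| 5 vs 15% | 91% | 99.7% |
| 10 vs 20% | 79% | 98% |
| 20 vs 30% | 63% | 90% |
| 30 vs 40% | 55% | 84% |
| 45 vs 55% | 51% | 80% |

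Example, 10 vs 20% with n = 196: (0.10 × 14 − 1.960 × 0.505) / 0.5 = 0.82, and Φ(0.82) = 0.79.

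**Precision does not need the planning inputs.** With 196 per condition, the 95% interval for a difference in proportions has a half-width of at most 1.96 × √(0.5/196) = 0.099. At 10 vs 20% it is 1.96 × √(0.25/196) = 0.070.

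**Aim 1 scale.** Assume two equally common grades, so that kappa = 2 × agreement − 1. Agreement rising from 80 to 90% is then kappa rising from 0.60 to 0.80. The variance of each kappa is (1 − κ²)/n, so with n = 196 the standard error of the difference is √((0.64 + 0.36)/196) = 0.0714. Then 0.20/0.0714 = 2.80 and power is Φ(2.80 − 1.96) = 80%. A kappa change from 0.50 to 0.60 has standard error √((0.75 + 0.64)/196) = 0.084 and power of 22%; with n = 392 it is 39%. These values illustrate that the two scales differ. They do not carry over to other numbers of grades, weights or patterns of disagreement, none of which the documents give.

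**Re-entries.** If 5 to 20% of examinations were re-entries (assumption), 392 examinations would come from 392 × 0.95 = 372 to 392 × 0.80 = 314 patients.

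**The case for a change.** The strongest case for a change is that two legitimate calculations, both using item 8's own alpha, power and 10%, differ twofold in total size, and that enrolment governs when the study ends. If 392 was meant per condition, stopping at 392 overall would leave about 51% power at mid-range base rates. A few sentences would remove the doubt at little cost.

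Much of the description stands: the inputs are missing, no other section supplies them, and having statisticians involved does not fill them in. The consequence does not follow. Item 8 states a minimum for the study without mentioning arms or doubling, so 784 arises only by fitting base rates backwards. A floor also does not prevent larger enrolment. Nothing in the documents says that base rates are mid-range, so the low-power rows are possibilities only.

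Two further arguments go beyond the text. That re-entering patients cannot be told apart is an inference from the reason given for the consent waiver; section 3h does not describe the data set or rule out a study code. What can be said is that no method of recognising re-entries is described. Nor can item 8 be taken to assume independent examinations: it names no test, section 3a makes trainees their own controls, and section 5c lists matched and repeated-measures methods.

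**Conclusion.** No change to the plan follows. The justification for 392 is incomplete, and a reader cannot attach the 80% power to a particular primary outcome. But the number is a correct result under at least two standard readings, and the text favours the total. Writing down the outcome, base rate, type of change, sidedness, test and label would document the calculation. The documents give no ground for thinking it would alter the target, the design or the analysis.

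Analysts can fill the remaining gaps sensibly. Agreement, prescription, confidence and repeat examination all attach to one examination, so the completed examination is the natural counting unit. A null result would be read from its confidence interval, at most about ±10 points for a difference in proportions with 392 in total, and for Aim 1 from the kappa difference with its interval. Neither requires the planning inputs.

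This rests on 1:1 allocation and on independent examinations in the calculations shown; clustering by trainee, patient or week is not covered here. It would be overturned by evidence, absent from these documents, that 392 was meant per condition or that the outcome it was sized for has a mid-range base rate.
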